5.3 Interruption due to COVID-19 Pandemic

The intervention period for BEAGLE was originally slated to begin in April 2020. However, on March 21, 2020, the governor of Illinois and mayor of Chicago issued a “stay-at-home” order to mitigate harm from the COVID-19 pandemic. This severely impacted regular primary care activities at Northwestern Medicine. As such, we chose to delay the start of the intervention until regular care resumed. The intervention was rolled out on September 1, 2020, and the look-back period for the study measures was adjusted to exclude data collected between March 1, 2020 and August 31, 2020. So, for example, study outcomes reported in December 2020 included the following 12 months of data: June 1, 2019 – February 29, 2020 plus September 1, 2020 – November 30, 2020.

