DM. Diabetes Overtreatment in the Elderly (DM) is defined as the having the most recent hemoglobin A1C during the measurement period or during the year prior to the measurement period (if no A1C obtained during the measurement period) of less than 7.0 among adults aged 75 years and older with a diagnosis of diabetes mellitus who have insulin or an oral hypoglycemic (e.g., sulfonylurea or meglitinide, Protocol Supplement 4, pg. 12) on their active medication list at the end of the study period. Patients are attributed to the primary care clinician with whom they had the greatest number of visits during the measurement period. The measurement period is the 365 days preceding the measurement date.

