10.4 Outcomes

10.4.1 Co-primary outcomes

This study has 3 co-primary outcomes, referred to as PSA, UA/UC, and DM (defined in Section 6 above). They capture the over-testing, over-screening, and over-treatment of older patients, who may need less care than they are receiving. The ICD-10 codes used to capture these co-primary outcomes are defined in detail in the Supplement to this document. These outcomes are computable clinical quality measures that are abstracted from the EHR. They were previously validated as part of pilot work for this study. These will be extracted from the EHR on a monthly basis, with data for each month representing a 365 look-back period.

An office visit will be eligible for inclusion in the outcome denominator if it meets the following criteria:

PSA. Men were eligible for the PSA over-screening measure if they were age 76 years or older and attended at least one visit in the 365 days prior to the measurement date (for example, 365 days prior to February 1, 2020) with a clinician included in the study. Eligible patients had no history of prostate cancer (determined via diagnosis or procedure code) and were not taking an androgenic agent or anabolic steroid as of the measurement date.

UA/UC. Women were eligible for the urine testing for non-specific reasons (UA/UC) measure if they were age 65 years or older and had an in-person ambulatory care visit with a participating clinician in the 365 days prior to the measurement date where a urinalysis and/or urine culture was obtained in the interval 24 hours before to 48 hours after the visit. If a woman had multiple qualifying visits in the 365-day window, only the first was included.

DM. Patients were eligible for the diabetes over-treatment measure if they were age 75 years or older with a diagnosis of diabetes mellitus and their most recent hemoglobin A1C in the 365 days prior to the measurement date was less than 7.0%. Patients were attributed to the primary care clinician with whom they had the greatest number of visits in the 365-day window.

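### Applying the March-August 2020 exclusion to the DM measure means some patients are classified on a superseded A1C, or drop out, in early intervention readings

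*Combined protocol and SAP*

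**What the plan says.** Section 5.3 explains that the start was delayed by the pandemic and states that "the look-back period for the study measures was adjusted to exclude data collected between March 1, 2020 and August 31, 2020". Its worked example says that "study outcomes reported in December 2020 included the following 12 months of data": June 2019 to February 2020, then September to November 2020. Nothing from the six gap months enters. The same section says "The intervention was rolled out on September 1, 2020", the day after the gap closes.

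Section 6.1 defines DM overtreatment as "having the most recent hemoglobin A1C during the measurement period or during the year prior to the measurement period" below 7.0, in a patient with insulin or an oral hypoglycemic "on their active medication list at the end of the study period". The prior year is used only if the measurement period holds no A1C. The nominal length is 365 days: "The measurement period is the 365 days preceding the measurement date".

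Section 10.4.1 makes a patient eligible if "their most recent hemoglobin A1C in the 365 days prior to the measurement date was less than 7.0" percent. It has no prior-year fallback, and it places the A1C threshold among the eligibility criteria.

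Neither 6.1 nor 10.4.1 exempts A1C results from the 5.3 exclusion, and 10.5 plans no sensitivity analysis on it.

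**The concern.** PSA and UA/UC rest on tests obtained within a window, so skipping months of disrupted care is a defensible way to keep twelve months of routine practice in view. DM is a current state. Disruption may mean that fewer A1C tests were done, but a result that was recorded in the gap is still the latest one. Removing it does not take pandemic activity out of a count; it puts an older value in place of the latest. In the intervention readings that older value is then paired with a medication list dating from after the gap.

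Two illustrative patients, both read at 1 December 2020:

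- A1C 6.7 in January 2020, 7.6 in July 2020, next test February 2021. This patient counts as below 7.0 although the chart showed 7.6.
- A1C 7.4 in January 2020, 6.6 in July 2020, no test since. Under 6.1 this patient is not counted as overtreated; under 10.4.1 the patient is outside the denominator.

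The error is absent from readings dated before the gap, largest in the first intervention readings, and fades as patients are retested. Section 10.5 models the outcome as a monthly series and tests a difference in monthly change, so a time-varying measurement error matters there.

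**Working it through.** **1. The plan's own window.** For the December 2020 reading, 1 June 2019-29 February 2020 is 274 days and 1 September-30 November 2020 is 91 days. 274 + 91 = 365, so the stated 12 months reproduces. The gap is 184 days.

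**2. Age of a pre-gap result at 1 December 2020.** Youngest (29 February 2020): 1 + 184 + 91 = 276 days. Oldest in the window (1 June 2019): 274 + 184 + 91 = 549 days.

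**3. Readings affected.** Take readings on the first of each month, 1 October 2020 to 1 March 2022 (18 readings), with k the number of months since 1 September 2020. The stitched window holds k months after the gap and 12 - k months before it, so it straddles the gap for k = 1 to 11 (1 October 2020 to 1 August 2021). That is 11 of 18. From 1 September 2021 (k = 12) it no longer does; later readings can be affected only through the 6.1 prior-year fallback.

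**4. Share affected (assumptions).** The documents give no A1C testing rate. Assume Poisson testing at r = 1 to 4 tests a year, and gap testing at g = 0.3 to 1.0 of normal. Classification on an older in-window result needs three things:

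- no test since 1 September 2020: exp(-rk/12)
- at least one test in the gap: 1 - exp(-0.5rg)
- at least one test in the pre-gap part of the window: 1 - exp(-r(12 - k)/12)

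The product of all three, in percent of DM patients:

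| r | 1 Dec 2020 (k = 3), g = 0.3 / 0.5 / 1 | 1 Aug 2021 (k = 11), g = 0.3 / 0.5 / 1 |
|---|---|---|
| 1 | 5.7 / 9.1 / 16.2 | 0.4 / 0.7 / 1.3 |
| 2 | 12.2 / 18.5 / 29.8 | 0.6 / 1.0 / 1.6 |
| 3 | 15.3 / 22.3 / 32.8 | 0.5 / 0.7 / 1.1 |
| 4 | 15.8 / 22.1 / 30.2 | 0.3 / 0.5 / 0.6 |

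The ranges are about 6-33% and 0.3-1.6%. The first two factors alone give the share whose true latest A1C lies in the gap: 11-38% at 1 December 2020. The difference is patients with no older in-window result, who drop out under 10.4.1. With the 6.1 fallback, 12 - k becomes 24 - k in the third factor, and the share classified on an older result is 9-37% at 1 December 2020 and about 1-10% at 1 August 2021.

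**5. Misclassified share.** Assume 15-30% of consecutive results fall on opposite sides of 7.0. At 1 December 2020, without the fallback: 0.057 × 0.15 = 0.9% and 0.328 × 0.30 = 9.8%, so roughly 1-10%. This is gross; errors run both ways.

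**The case against.** The exclusion is disclosed and deliberate, and it gives every measure the same twelve months of routine-care data. It affects only patients tested in the gap and not since; anyone retested after 1 September 2020 is classified on the true latest value. All shares rest on assumed testing rates. These points stand, and they limit the size of the problem. They do not give a reason to treat a recorded A1C as if it did not exist.

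A calendar 365-day A1C rule would also be a poor replacement. Suppose strictly yearly testing at random times, with gap testing halved. At 1 December 2020 the gap covers results 3-9 months old, so 6/12 = 50% of patients were due a test in it and 25% missed one. Their last A1C is 15-21 months old. Under 10.4.1 a calendar rule loses all of them, whereas the stitched window, reaching back 18 months, keeps half (12.5% of patients). That objection is met by keeping the stitched start date.

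A reader might infer three stronger things that the documents do not support:

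- **A very large share.** Exact six-monthly testing with no disruption puts the latest A1C in the gap for 5/6 = 83% of patients at 1 October 2020. But 5.3 itself reports severe disruption, and a result in the gap misclassifies no one unless an older in-window result exists and lies on the other side of 7.0.
- **Bias between arms.** This would follow if alerted clinicians rechecked A1C sooner. Section 5.1 describes the DM alert as encouraging a medication decrease and says nothing about rechecking.
- **Disagreement between alert and endpoint.** This depends on the alert's trigger criteria, which are in supplementary material not available here.

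**Conclusion.** The point holds for the DM measure. As written, 5.3 combined with 6.1 or 10.4.1 assigns some patients a status that a newer recorded result contradicts, and removes others for want of an A1C. Under 10.4.1 the error also changes who is in the denominator.

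The size given above is conditional on assumed testing and crossing rates. The net shift in the DM rate cannot be computed from the documents. It would be wrong to set the 1-10% against the 3.9-4.8% reductions in Table 1 of 10.2 as if both measured the same thing: one is gross misclassification, the other a difference between arms.

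The rule is the same in both arms, so the expected harm is mainly dilution of the DM contrast and a shared artefact that fades over the intervention period. This is a measurement flaw worth removing, not evidence that the comparison favours one arm.

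**What to change.** In 5.3, keep the stitched window's start date for DM but let A1C results from March-August 2020 count when the most recent value is selected. Widening the set of permitted results cannot leave a patient without an A1C who has one now, so no one loses eligibility for want of a result. Then:

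- apply the same rule when deriving the previously tightly controlled group in the safety outcomes (sections 8 and 10.4.2);
- report the gap-excluded version of DM as a sensitivity analysis in 10.5;
- reconcile 6.1 and 10.4.1 on the prior-year fallback, since it decides whether a patient with no in-window A1C is classified or dropped, and whether readings from 1 September 2021 are affected.

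The cost is a sentence in 5.3 and a small change to the date filter in the DM query; results come from the data warehouse already being queried. The downside is that the DM look-back is no longer handled identically to PSA and UA/UC, which the text should say openly.

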6. STUDY ENDPOINTS

6.1 Primary endpoints

Our team developed and validated by manual chart review three electronic clinical quality measures (one associated with each of the 3 study interventions). These measures will be abstracted from the EHR once a month for the duration of the intervention period. The three co-primary endpoints are:

PSA. The PSA screening in older men (PSA) measure is defined as the presence of a PSA laboratory result in the EHR during the measurement period among men aged 76 years and older at the start of the measurement period with at least one visit during the measurement period with a clinician included in the study and who are without a diagnosis or procedure suggesting a history of prostate cancer (Protocol Supplement 2, pg. 4). Patients on androgenic agents or anabolic steroids are excluded (Protocol Supplement 2, pg. 7). Labs constituting the numerator are provided in Protocol Supplement 2 (pg. 7). Patients are attributed to the primary care clinician with whom they have the greatest number of visits during the measurement period. The measurement period consists of the 365 days preceding the measurement date.

UA/UC. Urine Testing for Non-Specific Reasons (UA/UC) is defined as the absence of a diagnostic code for a specific genitourinary sign, symptoms or other potentially relevant indication (Protocol Supplement 3, pg. 8) among instances where a urinalysis (UA) and/or urine culture (UC) is obtained in the interval 24 hours before to 48 hours after a face-to-face ambulatory care visit by a woman aged 65 years or older with a qualifying clinician during the study period. Testing episodes are attributed to the clinician who ordered the test. Only UA and/or UC ordered by a qualifying clinician are included. Only the first testing episode in a measurement period is included in patients with multiple qualifying visits. The measurement period is the 365 days preceding the measurement date.

DM. Diabetes Overtreatment in the Elderly (DM) is defined as the having the most recent hemoglobin A1C during the measurement period or during the year prior to the measurement period (if no A1C obtained during the measurement period) of less than 7.0 among adults aged 75 years and older with a diagnosis of diabetes mellitus who have insulin or an oral hypoglycemic (e.g., sulfonylurea or meglitinide, Protocol Supplement 4, pg. 12) on their active medication list at the end of the study period. Patients are attributed to the primary care clinician with whom they had the greatest number of visits during the measurement period. The measurement period is the 365 days preceding the measurement date.

6.2 Secondary endpoints

We chose secondary endpoints related to the primary PSA, UA/UC, and DM outcomes. These were selected to identify other burdens on the healthcare system, and included:

- PSA
 - Prostate biopsy in older men
 - Prostate MRI in older men
 - New prostate cancer diagnosis in older men
- UA/UC
 - Total urinalysis use in women aged 65 and older
 - Total urine culture use in women age 65 and older
 - Antibiotic treatment in women age 65 and older (all oral UTI treatments)
 - Antibiotic treatment in women age 65 and older (nitrofurantoin and Fosfomycin only)
 - C. difficile infection in women age 65 and older

- Rash in women age 65 and older
- DM
 - Hypoglycemia requiring an urgent care visit (not emergency department) among eligible patients

We will also measure the three co-primary outcomes monthly during a follow-up period (months 19-30) to evaluate the persistence of any effects observed during the study period.

We will survey the clinicians who consent to participate in an online questionnaire about their attitudes about their experience with study interventions as well as their attitudes and beliefs about testing and treatment more broadly among geriatrics patients. See Baseline Clinician Survey and Follow-up Clinician Survey.

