2. BACKGROUND AND RATIONALE

2.1 Background on Overtreatment and Unnecessary Testing in Geriatric Populations

Despite strong recommendations from the American Geriatrics Society as part of the Choosing Wisely Initiative, sometimes clinicians do not follow best practices regarding ordering testing and treatments for their older adults that may lead to patient harm. These include: (1) testing and treatment for asymptomatic bacteriuria (ASB) in older women, (2) prostate specific antigen (PSA) screening in older men without prostate cancer, and (3) aggressive treatment with insulin or an oral hypoglycemic for older patients with type 2 diabetes.

Clinical decision support nudges, informed by behavioral economics and social psychology and delivered via EHRs, are promising strategies to reduce the misuse of services. Behavioral economics-informed interventions influence conscious and unconscious drivers of clinical decision making, are low cost to implement and disseminate, and can be incorporated into existing delivery systems. Our team has successfully employed these methods to the overuse of antibiotics for acute respiratory infections and has the necessary expertise in primary care practice, geriatrics, health informatics, social psychology, quality improvement, pragmatic trials and performance measurement to make this project a success. As our population continues to age, effective strategies to improve clinical care of older adults by reducing misused testing (e.g., urinalysis for ASB, prostate cancer screening with PSA) and treatment (e.g., overly-intense treatment of diabetes with insulin or other oral hypoglycemic) are critically needed.

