2.2. Study Rationale

Preliminary data. This study builds on a pilot study conducted at Northwestern University by the same study team, which was funded by the National Institute on Aging (R21 #____; clinicaltrials.gov identifier NCT03704389). The EHR nudge used here, presented as clinical decision support prompts, were designed and pilot tested as part of that study.

During 2017-2018, our team interviewed NM primary care physicians caring for older adult patients to identify potential drivers of overuse of testing and treatment. Clinician participants reported knowledge of the Choosing Wisely recommendations (e.g., “We’ve always known to be a little more lenient for elderly patients because of hypoglycemia and falls...”), a reliance on patient preference (e.g., “Some patients are very insistent or expectant that they would want to continue to get testing”), clinical uncertainty and an underestimation of harms (e.g., “Don’t want to over test her, but at the same time if she has treatable UTI want to treat her to get her some relief.”). Additionally, we found that clinicians often perceive discussions with patients about not ordering tests or treatments to be time consuming (e.g., “After long discussion, seems overwhelming majority of patients want to do the test. Given limits of time we have, I’ve been less detailed in discussion...”). Finally, the theme of clinical inertia or resistance to change was present (e.g., “If this patient is doing well, I might leave it [diabetes treatment] alone.”)

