5. STUDY INTERVENTIONS

5.1 Definitions of Study Interventions

Clinician education (control). An interactive educational module (15-20 minutes) covering the three targeted areas of overuse.

Clinical decision support plus clinician education (intervention).

Best Practice Advisories were programmed into Epic to present content to the clinician and feature functionality to add content to the encounter documentation. Clinicians attributed to clinics in the ‘CDS intervention + Education’ arm receive CDS alerts when conditions within a chart meet triggering criteria. For example, a CDS alert appears when a clinician places an order for a PSA test when the patient meets qualifying criteria (e.g., ≥ 76 years old, no prior prostate cancer). The CDS alerts encourage the clinician to cancel the order in the cases of PSA and urine testing or to decrease diabetes medication in the case of diabetes overtreatment (Table 1); however, they do not restrict clinical decision making in any way. If the clinician proceeds with the order for the PSA, urinalysis, or urine culture they are asked to enter text justifying the order. This justification is then included within the encounter report, visible to any clinician within the chart, under a heading titled ‘Testing Justification’. If the clinician does not enter a justification, the note “No justification given” is included in the encounter report.[9, 10] Images of the CDS presented to the clinicians for each alert and triggering criteria are included in the supplemental material. The EHR programming logic used in the pilot study was re-tested for this trial.

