8. SAFETY ASSESSMENTS

We did not study any safety endpoints related to the PSA primary outcome. The safety endpoints related to the UA/UC and DM primary outcomes were deemed serious adverse events, and included:

- EHR-identified ED or hospital care possibly due to UTI or sepsis among women 65 and over following an office visit
- EHR-Identified ED or hospital care possibly due to hyperglycemia among previously tightly controlled
- Poor diabetes control ($\text{HbA1c} > 9\%$) among individuals who were previously tightly controlled ($\text{HbA1c} < 7\%$)

The Principal Investigator will report any unanticipated events to the IRB as well as the Data Safety and Monitoring Board (DSMB) assembled for this study. When notified of an unanticipated event, the DSMB will convene and make a decision as to whether the study should continue. The IRB will also be notified of the DSMB's decision.

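### The only hypoglycemia outcome leaves out emergency department visits without a stated reason, while hyperglycemia is counted in emergency department or hospital care

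*Combined protocol and SAP*

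**What the plan says.** Section 6.2 lists a single secondary endpoint for diabetes: "Hypoglycemia requiring an urgent care visit (not emergency department) among eligible patients". Section 10.4.2 repeats it in the same words. Section 6.2 gives the purpose of the secondary endpoints: "These were selected to identify other burdens on the healthcare system". Section 3 describes the secondary outcomes as measures of patient safety.

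The diabetes safety endpoints, in Section 8 and again in Section 10.4.2, are "EHR-Identified ED or hospital care possibly due to hyperglycemia among previously tightly controlled" and "Poor diabetes control", the latter meaning HbA1c above 9% in patients who were below 7%. The urine-testing safety endpoint also uses acute care: "EHR-identified ED or hospital care possibly due to UTI or sepsis among women 65 and over following an office visit".

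Section 5.1 says that the diabetes alert encourages the clinician "to decrease diabetes medication in the case of diabetes overtreatment".

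**The concern.** A nudge towards less glucose-lowering treatment could plausibly move two things in opposite directions: fewer low-glucose events and more high-glucose events. The plan follows the second into the ED and the hospital. It follows the first only into urgent care. A reader weighing benefit against harm for the diabetes component would be comparing events from different care settings.

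Two consequences are at stake. A reduction in ED- or hospital-treated hypoglycemia would appear in no listed endpoint. And because the endpoint sees one setting only, a change in where patients seek care could pass for a change in how often hypoglycemia occurs.

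**Working it through.** **Step 1. Does another endpoint fill the gap?** All listed diabetes outcomes other than the co-primary, set side by side:

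| Outcome | Section | Care setting | Captures hypoglycemia in ED or hospital? |
|---|---|---|---|
| Hypoglycemia | 6.2, 10.4.2 | Urgent care; ED excluded | No |
| Hyperglycemia | 8, 10.4.2 | ED or hospital | No |
| HbA1c above 9% | 8, 10.4.2 | Laboratory value | No |

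The adverse event row in the Section 7.1 schedule names no hypoglycemia item. Nothing fills the gap.

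**Step 2. Does a stated purpose explain the exclusion?** If the secondary endpoints measure burden on the health system (Section 6.2), ED care is such a burden. If they measure patient safety (Section 3), ED-treated hypoglycemia is relevant to that too. Neither purpose explains leaving ED visits out. Data access does not explain it either, since ED and hospital care is to be identified from the EHR for two other endpoints.

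**Step 3. What can an urgent-care-only endpoint show?** Let R be the true ratio of all acute hypoglycemia, intervention to control. Let s0 and s1 be the shares seen only in the ED or hospital in the control and intervention arms. The ratio that the endpoint estimates is

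RR(urgent care) = R × (1 − s1) / (1 − s0).

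The shares and ratios below are assumptions; the documents give none.

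- Equal shares: RR(urgent care) = R. There is no distortion, only fewer events.
- No true change, ED share lower under the nudge (R = 1, s0 = 0.50, s1 = 0.25): 0.75/0.50 = 1.50, an apparent harm.
- No true change, ED share higher under the nudge (R = 1, s0 = 0.25, s1 = 0.50): 0.50/0.75 = 0.67, an apparent benefit.
- Half of control events in the ED or hospital, and only those events reduced, by a factor of 0.7: R = 0.50 × 0.7 + 0.50 = 0.85, but the urgent care count is unchanged, so RR(urgent care) = 1.00. A true 15% reduction is invisible.

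**Step 4. Precision, for illustration only.** The plan has no figure to reproduce. For rare events the standard error of a log odds ratio scales roughly as 1/√(fraction of events kept). This ignores clinic and provider variance, which does not shrink with the event count, so the multipliers are upper bounds.

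From Section 10.2 and Table 1: 6,600 diabetes patients, 60 clinics, intraclass correlation 0.017. That gives 3,300 per arm and 6,600/60 = 110 per clinic, hence a design effect of 1 + 109 × 0.017 = 2.853 and 3,300/2.853 ≈ 1,157 effective patients per arm. Assumed: acute hypoglycemia rate 0.5% to 2% in the control arm and, for power, the 2% rate, a relative risk of 0.7 in both settings and two-sided alpha 0.05.

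| Share only in ED or hospital | Control events counted (0.5% to 2%) | SE multiplier | Power, no design effect | Power, design effect 2.853 |
|---|---|---|---|---|
| 0% | 16.5 to 66 | 1.00 | 47% | 20% |
| 25% | 12.4 to 49.5 | 1.15 | 37% | 16% |
| 50% | 8.25 to 33 | 1.41 | 26% | 12% |
| 75% | 4.1 to 16.5 | 2.00 | 15% | 8% |

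The intraclass correlation was estimated for the power calculation of the co-primary outcomes and may not suit hypoglycemia, hence the two power columns. The direction is clear, but the size is unknown.

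**The case against.** The strongest reply is that the two lists have different jobs. Section 8 holds possible harms of the intervention, and for a nudge towards less treatment those are hyperglycemia and loss of control. Hypoglycemia is a possible benefit, so it belongs among the secondary endpoints. That stands: its absence from the safety list is no error, harm detection is intact, and under-measuring benefit mostly works against the nudge. It does not explain why the benefit is counted in one setting only.

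It is also fair that the parenthesis looks deliberate, that this is one of ten clinical secondary endpoints, and that a rationale could stand in the supplements or the protocol paper, which are not in the text available. Nothing in the documents suggests that the nudge changes the site of care, so Step 3 shows a possibility, not a prediction.

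Several stronger readings are tempting and not supported:

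- That the nudge is meant to prevent severe hypoglycemia. The stated aim is less overtreatment. Section 2.1 speaks of care "ordering testing and treatments for their older adults that may lead to patient harm" in general, and Section 2.2 names hypoglycemia only in an interviewed clinician's remark about being "a little more lenient for elderly patients because of hypoglycemia and falls".
- That ED-treated events are the most severe. This is reasonable, but the documents do not say it.
- That the exclusion makes a rare outcome rarer and sets off the convergence fallbacks in Section 10.5. No hypoglycemia rate is given, and that section says only that convergence may be a problem if events are sparse. Fewer events make the fallbacks more likely; no more can be said.
- That a specific loss of precision follows. Any figure rests on an assumed ED share.

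**Conclusion.** The concern holds as a gap in endpoint definition. The plan has one hypoglycemia outcome, that outcome excludes ED visits with no reason in the available text, and no other endpoint covers hypoglycemia in the ED or hospital. The secondary evidence on benefit and harm for the diabetes nudge therefore uses different care settings for each direction.

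The consequence is confined to that secondary evidence. The co-primary diabetes outcome, its model and its power do not depend on it. The loss of precision cannot be quantified from the documents. Adding ED and hospital events would make the outcome complete and guard against a change in care setting being read as an effect. It would not make the comparison well powered: under the assumptions in Step 4, power stays below 50% even with every event counted.

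**What to change.** Keep the urgent care endpoint as stated. Add hypoglycemia with urgent care, ED or hospital care, defined in the same eligible diabetes patients and drawn from the same EHR warehouse. Report both versions, and give the urgent care and the ED or hospital counts separately so that a shift between settings can be seen. If the exclusion was intended, also state the reason.

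The cost is one more code list and one more query. The hyperglycemia pull cannot simply be reused, because that endpoint is limited to patients who had been under tight control, whereas the hypoglycemia endpoint covers all eligible patients; the new query must run over the latter. It also adds one secondary outcome. Much of the document is written in the past tense (for example, data extraction in Section 11.2), so outcome data may already have been seen. The addition should therefore be labelled supplementary, or post hoc if that is the case, and should not replace the stated endpoint.
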